#### **F.3.3.2. Planned Subgroup Analyses**

We may conduct subgroup analyses to explore the possibility of heterogeneous intervention effects across theoretically/policy/socially-relevant subgroups of programs and/or residents, depending on the level of analysis. In program-level analyses, we may conduct subgroup analyses to investigate whether there was any intervention modification by characteristics that may include: baseline level of program activity regarding resident wellness or learning environment, geographic region, program size, baseline levels of resident burnout and/or mistreatment, gender balance or racial balance. In resident-level analyses, we may conduct subgroup analyses to investigate whether there were differential effects of Intervention for female versus male residents; for non-white versus white residents; or for burned-out versus non-burned out residents. We may also examine whether there was any intervention modification by region, residency year, or baseline wellbeing, for example. All subgroup analyses will be executed by means of regression models that include an interaction term between study arm assignment and indicators of subgroups of interest. Statistical tests on interaction coefficients will provide evidence for the presence or absence of effect modification. Subgroup analyses will not be executed by subgroup stratification.

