**Expected Outcome:** A pragmatic cluster-randomized trial will demonstrate that access to personalized, nationally-benchmarked data, along with an array of ready-to-implement interventions and implementation assistance, will (A) measurably improve the learning environment and resident well-being without (B) negatively impacting resident education or (C) patient care.

**Objective 3:** To refine the Wellness Toolkit by identifying successful context-specific interventions and expanding intervention access to the Control arm.

**Expected Outcome:** By examining specific initiatives implemented by programs as well as their successes and failures, we will be able to identify (1) particular interventions, (2) groups of interventions, or (3) configurations of interventions that are beneficial in certain contexts (e.g., large, urban programs and small, rural programs have unique needs requiring different interventions). Based on these data, the Wellness Toolkit will be refined, and access will be expanded to all participating residency programs.

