Using the constant estimated from the adjusted model as an estimate of the mean burnout score in Control (45.933) and the standard deviation of the Level-1 error component as the estimate of the standard deviation (9.027) around mean burnout scores in Control and assuming  $\alpha_{final}=0.0443$  for the final analysis, 80% power and  $ICC=0.012$ , we computed minimal detectable differences for a variety of hypothetical sample sizes, as reported in EXHIBIT D.8-B.

The scenario yielding the smallest detectable difference in adjusted mean burnout scores would be one in which there are 300 programs total, 150 programs in each arm with a mean of 25 residents per program. In this scenario, given our assumptions, we expect to be powered at 80% to detect a relative difference in mean burnout scores of -1.46%.

In a conservative scenario with 100 programs randomized to each study arm (200 programs total) and an average of 15 residents per program, we expect to be powered at 80% to detect a relative difference in mean burnout scores of -2.22%.

In a moderate scenario with 110 programs randomized to each study arm (220 programs total) and an average of 20 residents per program, we expect to be powered at 80% to detect a relative difference in mean burnout scores of -1.87%.

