#### EXHIBIT D.8.B Minimal Detectable Differences for Primary Analysis under Varying Sample Size Scenarios

Number of Programs (Clusters) per Arm	Number of Residents per	Usual Care Mean Burnout	Estimated Intervention	Minimal Detectable Difference	Relative Difference (%)

	Program (Mean Cluster Size)		Mean Burnout		
150	25	45.93	45.26	-0.67	-1.46%
150	20	45.93	45.19	-0.74	-1.61%
150	15	45.93	45.10	-0.83	-1.81%
125	25	45.93	45.19	-0.74	-1.61%
125	20	45.93	45.12	-0.81	-1.76%
125	15	45.93	45.02	-0.91	-1.98%
110	25	45.93	45.14	-0.79	-1.72%
110	20	45.93	45.07	-0.86	-1.87%
110	15	45.93	44.96	-0.97	-2.11%
100	25	45.93	45.10	-0.83	-1.81%
100	20	45.93	45.03	-0.90	-1.96%
100	15	45.93	44.91	-1.02	-2.22%

NOTES: Minimal detectable difference from adjusted estimate of mean burnout scores, assuming mean burnout T-scores in Usual Care=45.933, SD in both arms=9.027, ICC=0.012, alphafinal=0.0443 and power=80%, based on preliminary estimates in EXHIBIT D.8-B. Relative difference is expressed as a percent of Usual Care mean.

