#### F.3.1.2. Adjusted Analyses

Covariate adjustment in evaluations of randomized trials is generally done for purposes of increasing statistical efficiency by reducing variance within treatment groups. Covariate adjustment is also sometimes also undertaken on the basis of chance imbalance of baseline characteristics between study groups. Although programs will be randomized to treatment arms in this study, we anticipate considerable variation in the number of ABSITE respondents per program. In the 2019 ABSITE data, the average program had 23 resident respondents (mean=23.11, SD=11.15; coefficient of variation=48%), but the range spanned from a minimum of 3 residents per program to a maximum of 59 residents per program. Such dispersion in cluster sizes may lead to imbalance of resident characteristics

Thus, our analytic approach to evaluating our primary hypothesis will be to estimate a 2-level hierarchical linear model of the general form:

$$y_{ij} = \alpha_0 + \beta_0 TREAT_j + \beta_1 x_{1ij} + \beta_2 x_{2ij} + \cdots + \beta_k x_{kij} + \gamma_1 z_{1j} + \cdots + \gamma_m z_{mj} + \zeta_j + \epsilon_{ij}$$

where  $y_{ij}$  is the burnout T-score of resident  $i$  in program  $j$ ,  $TREAT_j$  is the study arm assignment of program  $j$ , and  $x_{1ij}$ - $x_{kij}$  are resident-level covariates and  $z_{1j}$ - $z_{mj}$  are program-level covariates to be adjusted for, including sampling stratification variables. In this model, under randomization of programs to study arms, the coefficient  $\beta_0$  is the adjusted population-averaged intent-to-treat estimate of the effect of assignment to intervention on mean resident burnout. A coefficient  $\beta_0 < 0$  that is statistically

significant with a one-tailed  $p<0.0443$  provides evidence supporting the effectiveness of the intervention over usual care. Other parameters in the model are the constant ( $\alpha_0$ ), coefficients on other resident-level covariates ( $\beta_1-\beta_k$ ), coefficients on program-level covariates ( $\gamma_1-\gamma_m$ ), program-level random intercepts ( $\zeta_j$ ) and individual-level errors ( $\epsilon_{ij}$ ).

Covariates may include variables listed in §E.3.: resident gender; resident relationship status; resident race; program type; program size; and randomization variables such as the quartile of program  $j$  ranked by 2019 program-level mean burnout scores. This list of covariates is subject to change.

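### Subgroup section treats an interaction test as able to show that effect modification is absent; under stated assumptions, power for an interaction the size of the detectable main effect is about 28% to 34%

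*SAP*

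**What the plan says.** SAP F.3.3.2 introduces the subgroup work as optional: "We may conduct subgroup analyses to explore the possibility of heterogeneous intervention effects". It names program-level candidates (among them baseline wellness activity, region, program size and baseline burnout) and resident-level candidates (among them gender, race and burnout status). Every subgroup analysis is to use an interaction between study arm and the subgroup indicator, and separate stratified analyses are ruled out: "Subgroup analyses will not be executed by subgroup stratification".

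The only statement on how the results are to be interpreted is "Statistical tests on interaction coefficients will provide evidence for the presence or absence of effect modification". The section gives no interval-based reading, no significance level for interactions, no power and no caution about null results. Section D.8.1 limits the power calculation to the primary endpoint, and Exhibit D.8.B covers only the main effect. The limitations in Section G do not mention subgroup power; G.4 warns only about multiplicity among secondary outcomes.

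**The concern.** A non-significant interaction coefficient has two possible explanations: the effects are similar across subgroups, or the data cannot separate them. The test alone does not distinguish the two. The sentence in F.3.3.2 allows the second to be reported as the first.

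This matters most where precision is low. If the trial finds a main effect and a subgroup interaction is not significant, the sentence would permit a statement that the effect does not differ between, say, large and small programs, or between female and male residents. The data might still be compatible with an effect confined largely to one of the two groups. The check below asks how wide that uncertainty is under the plan's own figures.

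**Working it through.** **Inputs**
- Exhibit D.8.B: "SD in both arms=9.027, ICC=0.012", alpha 0.0443, 80% power.
- Exhibit D.8.A, adjusted model: Level-1 variance 81.485, Level-2 variance 1.010.
- Section D.9: 209 programs enrolled (106 control, 103 intervention), so 104.5 per arm on average.
- Cluster size 20, as in the moderate scenario. D.8.1 gives a mean of 19.873 usable respondents per program in 2019.
- Normal quantiles: 2.011 (two-sided 0.0443), 1.703 (one-sided 0.0443), 0.842 (80% power).
- Assumption: subgroup shares are not given. A 50:50 split is used first, then 20:80.

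**Step 1. Reproduce the plan's figure.** For 110 programs per arm and 20 residents, the design effect is 1 + 19 × 0.012 = 1.228. The detectable difference is (2.011 + 0.842) × 9.027 × √(2 × 1.228 / 2200) = 0.86, as tabulated. All 12 rows of the exhibit reproduce to within about 0.005 with a two-sided 0.0443. One-sided, this row would be 0.77, so the exhibit is two-sided.

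**Step 2. Main effect at the enrolled size.** SE = √(2 × (81.485/20 + 1.010) / 104.5) = 0.312. Detectable difference = 2.853 × 0.312 = 0.89. (Using the exhibit's SD and ICC with 103 and 106 programs gives 0.88.)

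**Step 3. Interaction standard errors, 50:50 split.**
- Program-level factor: each arm's programs are halved, so SE = 2 × 0.312 = 0.624.
- Resident-level factor varying within programs: the program intercept cancels, so SE = √(8 × 81.485 / (20 × 104.5)) = 0.558. This takes the subgroup difference to be constant across programs; variation between programs would raise it.

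**Step 4. Power for an interaction of 0.89, two-sided 0.0443.**
- Program-level: Φ(0.89/0.624 − 2.011) = 28%.
- Resident-level: Φ(0.89/0.558 − 2.011) = 34%.

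The interaction needed for 80% power is 2.853 × 0.624 = 1.78 or 2.853 × 0.558 = 1.59.

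**Step 5. 95% interval half-widths.** 1.96 × 0.624 = 1.22 and 1.96 × 0.558 = 1.09. Both exceed 0.89, so an interaction estimate of exactly zero would not exclude a difference as large as the detectable main effect.

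**Step 6. Sensitivity.**

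| Setting | Program-level | Resident-level |
|---|---|---|
| 50:50, two-sided 0.0443 | 28% | 34% |
| 20:80, two-sided 0.0443 | 19% | 23% |
| 50:50, one-sided 0.0443 | 39% | 46% |
| 34 residents per program, at that design's own detectable effect (0.73) | 28% | 38% |
| 34 residents per program, interaction fixed at 0.89 | 39% | 53% |

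The 20:80 row replaces the divisor √(0.5 × 0.5) = 0.5 by √(0.2 × 0.8) = 0.4, giving SEs of 0.780 and 0.698. The one-sided row replaces 2.011 by 1.703. The last two rows use a 50:50 split, a two-sided 0.0443 test and the mean number of residents in Exhibit D.9 (about 34).

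**The case against.** The strongest reply is that this is an optional, exploratory paragraph. No interaction test is committed to, no alpha is assigned to one, and no trial decision depends on one. On that reading, *presence or absence* loosely describes the question the test addresses. Testing interactions instead of comparing stratified results is also sound practice. All of this stands and limits the consequence. It does not correct the sentence, which is the section's only guidance on interpretation.

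The power figures also need their conditions. The plan does not fix the sidedness of interaction tests; the primary test in F.3.1.2 must be "significant with a one-tailed" p below 0.0443. The plan gives no subgroup shares and no expected interaction size, so taking the detectable main effect as the yardstick is a choice. The program-level 28% follows from doubling the main-effect SE and would arise in any trial with about 80% main-effect power at this alpha. It illustrates a general limit and is not a defect peculiar to this design. The figures concern burnout only.

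Two stronger readings are tempting and are not supported:
- A reader might infer that most true differences in effect would be reported as absent. That depends on their size: interactions of 1.59 to 1.78 points would have 80% power under the base assumptions, and the plan says nothing about likely sizes.
- A reader might infer that Objective 3 would be misled because the F.3.3.2 subgroups are the contexts it wants to separate. Section B gives only one example, that "large, urban programs and small, rural programs have unique needs requiring different interventions", and its route is to study the initiatives programs implemented and how they fared. It does not mention arm-by-subgroup tests. Program size is a real overlap; gender, race and baseline activity are not named there.

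**Conclusion.** The point holds as a correction to interpretation. F.3.3.2 attributes to the interaction test a conclusion that a non-significant result cannot support, and no other section of the SAP corrects it. In every setting tried, power for an interaction equal to the detectable main effect is too low for a null test to be read as absence. The base figures of 28% and 34% rest on 104.5 programs per arm, 20 residents per program, the adjusted variance components, a 50:50 split and a two-sided 0.0443 test. Uneven splits lower them; a one-sided test or larger clusters raise them, to 53% at most in the settings shown. The primary estimate, its error control and the conduct of the trial are unaffected. What changes is what may be concluded from null subgroup results.

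**What to change.** In F.3.3.2:
- Delete the words *or absence*.
- Report each interaction as an estimate with a 95% interval, together with the subgroup-specific intervention effects from the same interaction model. This is compatible with the section's exclusion of stratified analyses.
- Describe a non-significant interaction as inconclusive unless its interval excludes differences judged important.

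A short statement of the low power, and use of the main-effect detectable difference as the margin for an important difference, would help but are optional. The cost is SAP wording and a few extra columns in the subgroup tables. No new data and no change to the design or primary analysis are needed.

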#### **F.3.3.4. Local Average Treatment Effects**

In a pragmatic trials such as this, there is little control of experimental conditions. In this trial, there is no condition in Control that restricts programs randomized to Control from engaging in any new activity or continuing any former activity related to promoting resident wellness or improving the learning environment. Although programs randomized to Intervention are offered information and other facilitative information to promote resident wellness and improve the learning environment, there is likewise no condition that requires programs randomized to Intervention to review the information

provided, much less adopt any recommended measures. In more traditional trial settings where adherence to study conditions can be even loosely defined, one can address issues of compliance heterogeneity by estimating local average treatment effects, which captures the effect of the intervention on compliers.

In this trial, we may adopt this approach and use instrumental variables (IV) to estimate the effect of intervention on outcomes among the subset of programs that acted in response to the intervention. Specifically, we will use study arm assignment to instrument implementation of a program organizational measure for promoting resident wellness and/or improving the learning environment that was not previously in place prior to the study intervention. We will then regress outcomes on instrumented implementation to obtain the average intervention effect among programs that would implement program improvement if offered the intervention. This analytic approach only uses variation in implementation that was due to random exposure of intervention to predict outcomes, and is thus free endogenous implementation due to self-selection on unobservables. We anticipate study arm assignment to serve as a valid instrument because: (a) study arm was randomly assigned; (b) study arm is assumed to have no effect on outcomes except through implementation of an intervention (exclusion criterion) and (c) study arm is predictive of implementing an intervention.

We may use two-stage least squares (TSLS) IV models for program-level estimation of local average treatment effects. First-stage F statistics will be examined to assess strength of the instrument in predicting implementation of program improvement interventions. We will not proceed if treatment assignment turns out to be a weak instrument.

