### **D.1.2. Justification of Pragmatic Nature**

The SECOND Trial is a pragmatic trial because programs will be offered feedback and strategies for improving the learning environment and resident well-being, but there will be no mandate by the Investigators to force Intervention programs to consider and/or act upon their feedback or prevent Control programs from acting upon theirs. Programs may attempt to improve their program measures at will, regardless of study arm. The only thing that distinguishes the Intervention from the Control Arm is the receipt of granular information on the learning environment, access to the Wellness Toolkit, and implementation support in the Intervention Arm.

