#### G.1. LIMITATIONS OF GENERAL STUDY DESIGN

- Participants in both Intervention and Control groups likely already have programs in place that address various aspects of resident wellbeing. As a pragmatic trial, we are not able or willing to request that participating programs deviate from what they have already implemented. Thus, the SECOND Trial intervention is properly seen as an offer of information (feedback reports and information on alternative interventions) on top of what may already be in place. Lack of a clean baseline and control group will attenuate any measurable effect of intervention towards zero.

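### The weak-instrument screen on the optional LATE analysis has no cut-off and, if new adoption differs only modestly between arms, partly restores the self-selection it is meant to remove

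*SAP*

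**What the plan says.** F.3.3.4 of the SAP makes the analysis optional: "We may use two-stage least squares (TSLS) IV models for program-level estimation of local average treatment effects". The exposure is implementation of a wellness or learning-environment measure that the program did not have before the study. Study arm is the only instrument.

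The plan then sets a diagnostic, "First-stage F statistics will be examined to assess strength of the instrument in predicting implementation of program improvement interventions", and a rule that follows from it, "We will not proceed if treatment assignment turns out to be a weak instrument". It does not say what value of F counts as weak.

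The stated merit of the approach is that it "is thus free endogenous implementation due to self-selection on unobservables". One of the three listed conditions is that "study arm is predictive of implementing an intervention"; the size of that relation is not given. The same section notes that "there is no condition in Control that restricts programs randomized to Control from engaging in any new activity" and that Intervention programs need not act on what they receive. D.1.2 says likewise: "Programs may attempt to improve their program measures at will, regardless of study arm".

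**The concern.** The observed difference in adoption is the true difference plus a chance imbalance in how inclined the programs in each arm were to adopt. A rule that reports TSLS only when the first-stage F is high favours samples in which that imbalance ran in Intervention's favour. If inclination to adopt is related to burnout for other reasons, the same imbalance also enters the burnout difference between arms. The reported ratio then moves toward the comparison of adopters with non-adopters, which is what the instrument was meant to avoid.

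At stake is the claim of freedom from self-selection. It is made for the method, but under the rule it need not hold for the estimates that reach the report. Without a cut-off, the decision on what is weak is also left until the data have been seen.

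**Working it through.** **Plan's own figures.** The SAP states no number for this analysis. As a check on the variance inputs, Exhibit D.8.B (110 programs per arm, 20 residents, SD 9.027, ICC 0.012, alpha 0.0443, power 80%) gives a minimal detectable difference of (2.011 + 0.842) × 9.027 × sqrt(2 × (1 + 19 × 0.012) / (110 × 20)) = 0.86, as stated.

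**Inputs from the SAP**
- 103 Intervention and 106 Control programs (Exhibit D.9).
- SD of a program mean with 20 residents (Exhibit D.8.A): unadjusted model sqrt(1.821 + 83.721/20) = 2.45; adjusted model sqrt(1.010 + 81.485/20) = 2.255.

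**Assumptions, because the SAP gives no figure**
- Weak means F < 10.
- Adoption rates as shown below.
- Correlation rho between adoption tendency and burnout as shown below.

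**Step 1: what the screen demands.** With SE = sqrt(p1(1-p1)/103 + p0(1-p0)/106), F ≥ 10 needs an observed adoption difference of about sqrt(10) × SE. The pass probability is about P(Z > (sqrt(10) × SE - true difference)/SE).

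| Adoption, Intervention vs Control | SE | Observed difference needed | Pass, by formula | Pass, simulated |
|---|---|---|---|---|
| 75% vs 60% | 0.0639 | 0.202 | P(Z > 0.82) = 21% | 21% |
| 80% vs 60% | 0.0618 | 0.195 | P(Z > -0.07) = 53% | 53% |
| 80% vs 50% | 0.0625 | 0.198 | P(Z > -1.63) = 95% | 94% |

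The screen therefore requires about 20 observed points whatever the truth. With a true difference of 15 points, only samples that overshoot pass; their mean observed difference is about 24 points.

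**Step 2: effect on the reported estimate.** Simulation, true effect -2.0, SD 2.45, adopters tending to have higher burnout:

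| Adoption | Unscreened median | Median after F ≥ 10, rho 0.3 | Median after F ≥ 10, rho 0.5 |
|---|---|---|---|
| 75% vs 60% | about -1.95 | -1.58 | -1.26 |
| 80% vs 60% | about -2.0 | -1.78 | -1.61 |
| 80% vs 50% | about -2.0 | negligible bias | negligible bias |

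Repeat runs differ only in the second decimal. With rho 0 there is no material bias. With the opposite sign of rho the screen exaggerates the benefit (75% vs 60%: -2.48 or -2.75).

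**Step 3: how much of the naive bias returns.** Separate simulation, true effect 0, SD 2.255, Control adoption 50%, rho -0.6, F > 10. The naive bias is that of the ordinary regression on adoption.

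| True difference | Passes | Screened median / naive bias | Unscreened median / naive bias |
|---|---|---|---|
| 5 points | 1% | 1.650/2.156 = 77% | 1.330/2.156 = 62% |
| 10 points | 5% | 1.280/2.145 = 60% | 0.394/2.145 = 18% |
| 15 points | 18% | 0.839/2.128 = 39% | 0.053/2.128 = 2% |
| 20 points | 44% | 0.494/2.102 = 24% | about 0 |
| 30 points | 94% | 0.060/2.020 = 3% | about 0 |

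The fractions are similar at rho -0.3. A looser cut-off of F > 3.89 lowers them to 46% at 10 points and 9% at 20 points.

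**Step 4: intervals.** The unscreened Anderson-Rubin set covers 95% in every setting, including no true first stage. Reported only after F > 10 at rho -0.6, its coverage falls to 69%, 78% and 86% at 0, 5 and 10 points. Adding the set while keeping the screen would therefore not solve the problem.

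**The case against.** A reader might infer that the complier estimate will be reported mainly when adoption differed by luck, and that the self-selection bias comes back whole. The SAP does not support that. It expects arm to predict implementation, gives Intervention alone the Toolkit, granular reports and implementation support, and bars sharing of the Toolkit during the trial. Nothing places the trial in the small-difference case, and at 80% versus 50% the screen is almost harmless. Except near a nil first stage, only part of the bias returns.

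A reader might also cite G.1, "Lack of a clean baseline and control group will attenuate any measurable effect of intervention towards zero", as evidence of a small adoption difference. That sentence concerns measures already in place, whereas the exposure in F.3.3.4 is a measure not previously in place. Only D.1.2 and F.3.3.4 itself bear on new adoption, and they show that a small difference is possible, not that it is expected.

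Three further objections stand:
- In the Step 2 settings the ordinary TSLS 95% interval still covers 92% to 97% after screening, and the worst shift (about 0.75) compares with a median standard error of about 1.4. Marked under-coverage needs a stronger correlation or a nearly nil first stage: at rho -0.6 it is 72%, 80%, 88% and 93% at 5, 10, 15 and 20 points.
- Merely deleting the rule would not be enough. At 65% versus 60% the unscreened TSLS median is itself about -1.3 or -0.8 against a true -2.0. The authors' worry about weak instruments is sound.
- The analysis is optional and secondary to intention-to-treat, and the screen looks at adoption, not at burnout.

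**Conclusion.** The point holds conditionally. The rule has no cut-off, and it biases what is reported if two things are true together: the real difference in new adoption is below roughly 20 points with 209 programs, and adoption tendency is related to burnout. At 15 to 20 points about 40% to 24% of the naive bias returns; at about 30 points or more, or with no such relation, the effect is negligible. These sizes rest on an assumed cut-off of F = 10 and on assumed adoption rates and correlations. The SAP supplies none of these, so it cannot be said which case will apply. Within those limits, the claim of freedom from self-selection does not fully hold for the estimates that pass the screen. This is a low-stakes improvement to an exploratory analysis, with no bearing on the primary result.

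**What to change.** Replace the sentence "We will not proceed if treatment assignment turns out to be a weak instrument" with text to this effect: if the LATE analysis is done, the adoption difference between arms and the first-stage F are reported in all cases; inference rests on the Anderson-Rubin 95% confidence set, with no screen on F, and the set is reported even when it is wide or unbounded; the TSLS point estimate appears only beside that set and is flagged as unreliable when the first stage is weak, with the F value that triggers the flag stated in advance.

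With one instrument and one exposure the set is simple to obtain. It contains every value b for which a regression of (outcome - b × adoption) on arm and strata does not reject a zero arm coefficient.

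The cost is a few lines of SAP wording and one extra command. The drawbacks are that the set may be unbounded when the arms barely differ in adoption, that its test of zero effect repeats the intention-to-treat test, and that it still needs the assumption that arm affects burnout only through implementation.
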